### ***C2 Rationale for the Selection of Outcome Measures***

As detailed above, we'll be examining uptake of the mobile mental health platform compared to referral to usual care, as well as effectiveness of the platform in reducing the number of individuals with mental health disorders; reducing disorder-specific symptoms; and improving quality of life and functioning. These are critical outcomes as they will tell us whether the mobile mental health platform is not only more likely to be used by students (uptake) but also whether it is effective on several dimensions.

---

We also propose several mediators, which fall into: 1) primary intervention targets/mechanisms, considered most essential to outcomes (some of which are transdiagnostic and some disorder-specific; and 2) other mediators—early engagement in services and rapid response. CBT theory posits that the most important ways to change symptoms are by changing cognitions and/or changing behaviors. Thus, our transdiagnostic targets are decreased dysfunctional cognitions and increased use of CBT skills. Empirical support for cognitive changes suggests that they are central to reduction in anxious and depressive symptoms. For EDs, although only a few studies have examined change in cognition, it is worth including given its emphasis in CBT theory. There is evidence that acquisition of CBT skills (e.g., challenging thoughts) is another critical target at least for anxiety and depression. Our disorder-specific, evidence-based targets are as follows: reducing avoidance, associated with changing anxiety; increasing behavioral activation, associated with reducing depressive symptoms; and reducing dietary restraint and weight/shape concerns for reducing EDs. We will examine whether the mHealth platform leads to change in the targets listed above and whether target change is associated with clinical benefit. Use of any potentially helpful services (e.g., Lantern, self-help, face-to-face therapy, medication) is also likely to lead to change, particularly in the first 6 weeks. Thus, while not a specific target of intervention, early engagement in help services is a potential mediator of symptom reduction and will be tested. Rapid response in symptoms, with rapid response usually defined as  $\geq 50\%$  reduction in symptoms occurring within the first 4-6 weeks of treatment, predicts longer-term outcome in anxiety, depression, and EDs and is considered a mediator. Within-mobile program indices will be tested as predictors of outcome, including sessions completed, number of messages sent by user and coach, techniques completed, time spent with the program, and coach personalization (i.e., assessed through users' perception and coding a subset of messages. Finally, data will be used to explore moderators—subgroups for whom further tailoring or more intensive services are needed in future iterations. Moderators exploratory and based on prior work; they are: gender, race/ethnicity, expectancy/credibility, symptom severity, duration of problem, comorbidity, disorder for which the person sought treatment, degree of cognitive distortion, impairment, family income, and motivation.

## **D Study Design**

### **D1 Overview or Design Summary**

At each of the participating campuses, we will recruit students from the undergraduate population. Some campuses may decide to provide us with a random sample (requesting from the Registrar [or equivalent campus unit] which is oversampled by gender, race/ethnicity, and socioeconomic status [e.g., Pell grant recipients] to ensure that participant samples are diverse and representative on these dimensions).

Students will be recruited via emails to their campus email address to participate in the screen.

---

Students will be asked at the start of the screen if they would like to opt out of receiving information about potential future studies. We will create an entire new registry of students from those who **do not select to opt out** of future studies, ensuring we will not be able to contact those who opted out of future contact from the new registry.

Following the screen students will receive personalized feedback about their results. The personalized feedback will be automated through Qualtrics, allowing for an efficient yet individualized feedback approach. The personalized feedback will include either an end of survey message thanking the individual for their participation (and a referral for treatment if applicable) or an invitation to participate in the full study as follows:

1. No symptoms or low risk for depression, anxiety, and EDs - they will not be eligible to participate in the next phase of the study.
2. Low risk with trauma, insomnia, or substance abuse - receive referral for clinical evaluation and intervention.
3. At high risk for or with clinical anxiety, depression, or an ED not currently in treatment; own a smartphone - will be invited to participate in phase 2 of the study.
4. At high risk for or with clinical anxiety, depression, or an ED currently in treatment and/or without a smartphone - will be encouraged to continue in treatment provided with a referral for clinical evaluation and intervention.
5. Anorexia nervosa - receive referral for clinical evaluation and intervention.

Following the personalized feedback, students meeting study eligibility criteria will receive a brief statement of eligibility for and description of the study purpose and duration, activities involved, and assessment time points. Students will be asked to confirm their willingness to continue. If they agree students will be asked for their email address and phone numbers, and will be provided a link to the Phase 2 survey. After giving online consent, participants will be randomized via a code through Qualtrics into one of two conditions:

- 1) Intervention: receiving access to our mobile coached self-help program for 6 months.
- 2) Control: Receiving information on how to receive treatment at the student's counseling center on campus.

Participants will then complete the baseline survey, which will assess treatment expectancy/credibility, cognitive distortion, impairment/quality of life, motivation for treatment, and mental health treatment utilization. After completing these measures students will be made aware of the condition they were randomized into and asked to complete a short Treatment Credibility and Expectancy Questionnaire.

Individuals who choose not to continue will receive their screen feedback through Qualtrics, a recommendation to seek care, and a campus-specific list of resources.

After completing the baseline survey participants will receive an email and text message with information about their screen responses and either a link to the mobile intervention or information on how to access clinical services, based on their randomized condition. Individuals who screen positive or at high risk for more than one of the three mental health disorders (anxiety, depression, EDs) will be asked to select which problem is most bothersome or impairing to their everyday functioning, which has been shown to correlate with provider ratings, and will then be directed to focus primarily on that problem using either the mobile app or in-person services.

---

All students in the usual care condition will receive a recommendation to seek care and will be given a list of resources available through their respective health or counseling center, including contact information to make an appointment and any other relevant resources on campus. Participants who will be completing the mobile interventions will be given a link to the program, hosted on a platform by our technology partners SilverCloud Health, and a program description. They will also be provided with instructions to download the SilverCloud Health program app, through which they can access the intervention, as well. Students are encouraged to log in to the intervention, create an anonymous username and password, and begin the program.

Both intervention and control groups will be asked to complete assessments at 6 weeks, 6 months, and 2 years after completing the baseline screen. 6 week assessments will ask participants to complete assessments of anxiety, depression, EDs, motivation for treatment, and mental health treatment utilization. The 6 month and 2-year follow-ups will include assessments of anxiety, depression, EDs, comorbidities, impairment/quality of life, motivation for treatment, mental health treatment utilization, and screening and treatment feedback. In addition, alternate contact information will be requested at baseline, 6, and 12 month follow-ups in order to maximize the likelihood that participants can be reached at the next follow-up assessment, including cell phone number for receiving SMS text-message reminders for follow-up surveys to be sent from the Qualtrics platform. Follow-up emails and SMS may also use images or other media to increase the students' attention and likelihood of response. In order to increase the response rate at 2-year follow-up the study team may call participants to remind them to complete the survey, the study team may leave a voicemail if the participant does not respond. All assessments will be conducted using Qualtrics survey platform.

Participants will be compensated by receiving an electronic gift card for completing the Baseline (\$5), 6 week (\$5), 6 month (\$10), and 2-year (\$20) follow-up assessments. Participants will be entered into a sweepstakes to win one of five \$50 gift cards after completing the Baseline, 6 week, 6 month, and 2-year surveys. In addition, once participants complete all four surveys, they will be entered into a sweepstakes to win one of ten \$100 gift cards.

All students who receive a recruitment email will be automatically entered into a sweepstakes for one of 40 \$100 electronic gift card prizes.

In order to assess mental health treatment utilization, in addition to assessing this via self-report, we will obtain aggregate counts of participants in therapy from campus counseling/health centers, by random assignment group at baseline, 6 months, and 2 years. To assess academic outcomes, including term by-term GPA and enrollment status (to assess drop-out), at the end of the 2 years we will obtain aggregate data of participants from Registrars by semester/term to include GPA and attrition rate by condition.

## **D2 Subject Selection and Withdrawal**

---

## **2.a Inclusion Criteria**

Screening survey inclusion criteria: Undergraduate students at participating colleges and universities who are 18 years old and older.

### Full study inclusion criteria:

- Students who screen has high risk or clinical/subclinical for anxiety, depression, and, EDs
- Students who are not currently in treatment, i.e., in the past month.
- Own a smartphone.

Students who endorse suicidal ideation in the baseline screening assessment will be given a referral to seek in-person care, however, we decided not to exclude students with suicidality, given that only 20-40% of college students with mental health problems receive treatment. As such, we deemed it insufficient to exclude such individuals from receiving the intervention and only providing an in-person referral, given the goal of this proposal to narrow the treatment gap for mental health problems among college students.

## **2.a Exclusion Criteria**

For the full study we will exclude students who do not own a smartphone since the intervention is a mobile app. We will also exclude students who are currently engaged in mental health treatment given the goal to increase access to services for those not receiving help.

## **2.b Ethical Considerations**

All key personnel involved in the design or conduct of research involving human subjects will receive the required education on the protection of human research participants prior to the start of the study. Participants will be informed that they do not have to answer any questions that make them uncomfortable. There are minimal risks for participants in the mobile health intervention. Coaches in SilverCloud Health will be recruited at the study four participating sites. Coaches will be students in a graduate program in psychology, counseling, or social work. Coaches will be trained and under the close supervision of a coach supervisor, at WUSM and PAU who licensed psychologists, as well as the Fidelity Monitoring Center.

Given national data showing that nearly 10% of students have seriously considered suicide in the past year and that rates of suicide on university campuses continue to increase, suicidality will be consistently monitored throughout the study, including within the mobile intervention itself and through the completion of the baseline and 6-week, 6-month, and 2-year follow-up assessments. Students who endorse any suicidality on these assessments will receive immediate follow-up, including a referral to seek in-person care. Despite the perceived risk that assessing suicidality will increase suicidality, research supports that asking about this does not increase suicidality and, among those who may endorse active suicidal plans or intent, may lead to improvements in health seeking behaviors and increased safety. Notably, we decided not to exclude students with suicidality, given that only 20-40% of college students with mental health problems receive treatment. As such, we deemed it insufficient to exclude such individuals from receiving the intervention and only providing an in-person referral, given the goal of this proposal to narrow the treatment gap.

---

Participant safety is of utmost clinical import, and several safety precautions and procedures will be implemented.

- 1) SilverCloud Health flags and notify coaches when a user responds positively to the PHQ-9 item about suicidality. Coaches will monitor the platform weekly to assess for significant changes in symptoms (e.g., increased purging). Any participant deemed unsafe or needing more intensive clinical intervention will be given a referral by their coach as well as contacted directly via telephone. Appropriate follow-up (e.g., contacting the university's on-call clinical staff or local police) will be implemented if participants are deemed to be at imminent risk and no response is provided by the participant indicating their safety. This protocol is to safeguard against concerns with keeping individuals in guided self-help care when more intensive services are warranted.
- 2) Individuals who remain in the clinical symptom range, in both the intervention and control conditions, at the 6-month or 2-year follow-up assessments, will be offered a referral for in-person treatment. For individuals in the intervention condition, in line with a stepped care model, those who do not demonstrate symptom improvement by 6 weeks will be referred to in- person care but can still engage in the program.

In the case of imminent risk, such as in the extremely rare case of a user reporting plans of suicide or homicide, there are several steps that coaches for students engaging in the mobile program are mandated to take as mandated reporters. First, coaches contact a coach supervisor and the Fidelity Monitoring Center either by phone or an email marked URGENT to consult about how to proceed as soon as possible. If coaches do not receive a response within an hour, they will reach out to a back-up coach supervisor. Second, coaches identify the appropriate local agency such as the campus police at the user's college or university to prepare for possibly making a report. Next, they provide the user with a variety of emergency options such as counseling center information, suicide hotline phone number, emergency room location, or local police information and encourage clients to seek additional support or hospitalization through these options. Coaches also gather relevant information by reviewing the coaching record for all identifying information available such as name, age, phone number, and email address to provide to the agency when making a report. If it is deemed appropriate by the coaching supervisor, coaches call in the report as soon as possible to the identified local agency. They also follow up with the user, express concern, provide support, and let him/her know a report has been made. In addition, coaches follow up with the coach supervisor and the Fidelity Monitoring Center via email to let him/her know the report was made. Finally, coaches continue to monitor the user for emerging or worsening risks, as demonstrated by information the user inputs into the program or messages to the coach, and they continue to keep in close contact with the coaching supervisor. Should the user continue to worsen and be deemed at continued imminent risk, the coach and coach supervisor may make a decision to withdraw the participant from the program.

In the case that individuals endorse criteria for possible AN (low weight and significant weight shape concerns) at the 6-month or 2-year follow-up assessments, they will be offered a referral for in-person treatment.

The Fidelity Monitoring Center will conduct fidelity checks on the coaching data from SilverCloud Health to ensure that coaches are following protocol (e.g., referrals given if lack of symptom improvement). In general, the Fidelity Monitoring Center will oversee regular review of coaches using quantitative and qualitative metrics that include tone and

---

style (authentic, personalized) of their interactions with clients, content (depth, goal orientation), efficiency (response time), user engagement, outcomes, and accuracy rate for risk management. Coaches that do not meet the metrics will be put on a performance improvement plan and may be terminated if improvement is not demonstrated.

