Participants completing the mobile intervention will receive the support from a coach. Their role includes supporting and enhancing user motivation; monitoring progress; facilitating goal setting and offering accountability; providing feedback on technique usage and encouraging practice; answering user questions; and monitoring for/responding to clinical risk. Communication with users is primarily via two-way, asynchronous messaging, with optional, supplementary phone calls to enhance goal setting. Coach messaging is done via a web-based "dashboard," and delivered to users within the SilverCloud Health app. Coaches have participants' baseline screen results so they can personalize treatment and help the user apply skills learned to comorbid problems. Moreover, coaches will monitor symptoms using the following assessments built into the SilverCloud Health programs:

- 1) For individuals with depression, depression is assessed weekly using an abbreviated version of the measure used for assessing depression at baseline (i.e., PHQ-2).
- 2) For individuals with anxiety, anxiety is assessed weekly using a short, validated measure of anxiety (i.e., GAD-2).
- 3) For individuals with eating disorders, weekly monitoring includes three questions based on the EDE-Q assessing eating disorder behaviors (i.e., binge eating, purging) and weight/shape concerns.

Note: When individuals have more than one of these problems, they complete weekly monitoring for each comorbidity.

If the coach feels the online program cannot adequately address comorbidity, participants are referred to appropriate campus/community resources.

The program will be accessible via smart phone app or their desktop. Program access will be password protected.

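### The coach alert depends on the PHQ-9 suicidality item, but no listed in-program check is described as containing that item, and no in-program PHQ-9 schedule is given

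*Combined protocol and SAP*

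**What the plan says.** Section D2 2.b sets out the safety precautions, and the first begins: "SilverCloud Health flags and notify coaches when a user responds positively to the PHQ-9 item about suicidality". Section 2.e, Risks and Benefits, repeats it. Section 2.b also commits to more than survey-based surveillance: "suicidality will be consistently monitored throughout the study, including within the mobile intervention itself", in addition to the baseline and follow-up assessments. Students with suicidal ideation are deliberately not excluded.

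Section D3 describes what the program asks. It says that "coaches will monitor symptoms using the following assessments built into the SilverCloud Health programs" and then lists three weekly checks:

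- Depression: "an abbreviated version of the measure used for assessing depression at baseline (i.e., PHQ-2").
- Anxiety: "anxiety is assessed weekly using a short, validated measure of anxiety (i.e., GAD-2").
- Eating disorders: "weekly monitoring includes three questions based on the EDE-Q assessing eating disorder behaviors", plus concern about weight and shape.

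Users with more than one problem complete the check for each. The same section gives coaches the role of "monitoring for/responding to clinical risk".

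Table 3 in E1 names the PHQ-9 as the depression screening measure. The schedule in E2 places depression assessment at baseline, 6 weeks, 6 months and 2 years, with every survey run in Qualtrics. Program access lasts 6 months (D2 2.d).

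**The concern.** The stated trigger and the stated in-program measures do not meet. The alert needs an answer to a particular PHQ-9 item, yet the listed weekly checks are shorter or different instruments. A site that built the weekly checks exactly as D3 lists them could leave the trigger question unasked between surveys and still believe that the monitoring promised in 2.b was in place.

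At stake is the opening element of the first listed safety precaution, in a trial that knowingly enrols students with suicidal ideation. The protocol gives no safety reason for holding back the question; it says that "research supports that asking about this does not increase suicidality".

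**Working it through.** The plan states no figure on this point, so there is none to reproduce. The check is a cross-reading followed by a short calculation of the possible gap.

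**Step 1: trigger against listed content**

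| Track | Weekly check (D3) | Described as including the PHQ-9 suicidality item? |
|---|---|---|
| Depression | PHQ-2 | No; called only an abbreviated form of the baseline measure, and its items are not printed |
| Anxiety | GAD-2 | No; described as a measure of anxiety |
| Eating disorders | Three EDE-Q-based questions | No; described as covering bingeing, purging and weight or shape concern |
| More than one | Combination of the above | No item is added |

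The mismatch is clearest on the anxiety and eating-disorder tracks, where D3's own description settles the content. On the depression track it rests on reading the two-item form as lacking the suicidality item, because the protocol does not reproduce the instrument.

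**Step 2: does any other section give an in-program PHQ-9 schedule?** None does. The intervention-period column in E2 marks only treatment process and coaching fidelity. That column omits the weekly checks as well, so its silence is not conclusive, but it does not fill the gap. Section G1 says that suicide-risk data from Qualtrics go to the platform, without stating timing or repeat transfers.

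**Step 3: longest scheduled gap if the item is asked only in Qualtrics**

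Inputs: surveys at 6 weeks and 6 months after the baseline screen (D1); access for 6 months (D2 2.d), taken as 26 weeks.

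- 6-week survey completed: 26 − 6 = 20 weeks.
- 6-week survey missed: 26 − 0 = 26 weeks.
- Weekly checks strictly between the two surveys: weeks 7 to 25, so 25 − 7 + 1 = 19.

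These are upper bounds. They apply only if the platform asks no suicidality item between surveys, and only to participants still using the program.

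**The case against.** The best reply is that this is a reporting gap. The alert is described in the present tense as a platform function, and 2.b says that monitoring takes place inside the intervention. Both presuppose that a PHQ-9 is given there. The D3 list concerns symptom monitoring and does not claim to be complete, and risk is handled separately in 2.b. A team following the whole protocol would implement those statements too. All of this stands as far as it goes. A reader might infer that the alert can never fire or that the program never asks about suicidality; the documents do not support that. Nor does the reply close the gap, because no interval or track is stated anywhere, and a safety trigger with no stated schedule cannot be audited.

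A second reply points to the other safeguards: suicide-risk data passed to the platform (G1), weekly coach review, referral when there is no improvement by 6 weeks, fidelity review of risk management (2.b), messages and optional calls (D3), adverse-event monitoring (E2, Reporting Procedures) and the surveys. These are real. Apart from the surveys, they depend on what the user discloses, on other symptoms or on data already collected. None is described as a scheduled question about ideation asked within the program after baseline.

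A third reply is that students with ideation are in both arms and that controls have no in-program monitoring at all. That is correct. The point is that the intervention arm should receive the monitoring it is promised; it does not show that this arm is less safe than control.

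**Conclusion.** The point holds as an internal mismatch that should be fixed. The alert depends on the PHQ-9 suicidality item, the listed in-program checks are not described as containing it, and its in-program timing and tracks are unstated. If the item is in fact asked only in the surveys, the scheduled gap is up to about 20 weeks, or about 26 weeks when the 6-week survey is missed. If the platform already asks it at a short interval on every track, the gap is smaller and the defect is one of documentation.

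A reader might want to turn this into a count of users exposed. The documents give neither an allocation ratio nor a projection of program uptake, and they do not say how many users would develop new ideation, so no such figure can be supported.

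**What to change.** Make sure that the PHQ-9 suicidality item, or an equivalent single item, is asked inside the program on all three tracks at a fixed short interval, and tie the coach alert to that item. Unless the platform already does so, add it to the existing weekly check; this matches the current rhythm of coach review and needs no new contact point. For users who complete the check, the longest scheduled gap then becomes one week. If the platform already asks the item on all tracks at a short interval, state that interval in D3. Section 2.b should also say that this reaches only participants who use the program; for the others, the surveys remain the only scheduled question.

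The costs are:

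- One extra item per weekly check, up to about 26 per user over 6 months, a platform setting, and an amendment to D3 and 2.b.
- Coach time. The positive rate is not given in the documents. If 1% to 10% of checks were positive (an assumption), 100 active users would generate 0.01 × 100 = 1 to 0.10 × 100 = 10 alerts a week.
- Some difference in the intervention between waves if the change is made mid-trial, since campuses enter in staggered waves (Study Timetable).
- Possibly more in-person referrals in the intervention arm only. Count the referrals that the alert triggers, and note them when service use by arm (D1), costs and 2-year case status (F3) are interpreted.

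Randomization and endpoint definitions do not change.

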## **2.b Reporting Procedures**

Because the online interventions follow standard practice guidelines that have been used in research trials without significant adverse events, we do not anticipate any significant adverse events. However, coaches will be trained to monitor for adverse events, including Serious Adverse Events (SAEs) such as deaths, hospitalizations, and life threatening events and Unanticipated Problems (UPs), and will report any potential adverse events immediately upon their identification to the FMC. We will also monitor for adverse events at all follow-up assessments and via all other communication with study participants. Any potentially adverse events will be evaluated by the PIs within 72 hours. Serious adverse events will be promptly reported to the study IRB. Study-related serious adverse events will be reported to the NIMH within 2 weeks; all others will be included in the annual report to the NIMH.

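### Read literally, the general referral offer at 6 months and 2 years omits participants, in both arms, who are newly in the clinical range at that visit

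*Combined protocol and SAP*

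**What the plan says.** Among the safety precautions in D2, 2.b Ethical Considerations, an in-person referral is offered to "Individuals who remain in the clinical symptom range, in both the intervention and control conditions, at the 6-month or 2-year follow-up assessments". D2, 2.e Risks and Benefits repeats the sentence unchanged. No other section gives a broader general offer at those two visits.

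The other routes to a referral, or to something close to one, are narrower:

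- **Suicidality, both arms, any assessment** (D2, 2.b): "Students who endorse any suicidality on these assessments will receive immediate follow-up", which includes a referral.
- **Possible anorexia nervosa** (D2, 2.b): the trigger reads "In the case that individuals endorse criteria for possible AN (low weight and significant weight shape concerns) at the 6-month or 2-year follow-up assessments", and a referral is then offered.
- **6-week rule, intervention arm** (D2, 2.b): "those who do not demonstrate symptom improvement by 6 weeks will be referred to" in-person care.
- **Coach judgement** (D2, 2.b): "Any participant deemed unsafe or needing more intensive clinical intervention will be given a referral by their coach". Coaches serve users of the mobile program, and D1 describes that arm as "receiving access to our mobile coached self-help program for 6 months".
- **Usual care at entry** (D1): "All students in the usual care condition will receive a recommendation to seek care and will be given a list of resources".
- **Adverse events** (E2, 2.b Reporting Procedures): "We will also monitor for adverse events at all follow-up assessments". This promises monitoring, not a referral.

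**The concern.** Someone can *remain* in the clinical range only after having been there. Table 3 in E1 keeps a separate stratum of students at high risk for at least one condition with none at clinical level, and F1 plans that stratum as half of the completers. F3 expects new cases, since it tests prevention as well as reduction of disorders. The outcome would therefore count a student who becomes clinical during follow-up, while the referral rule, as worded, would not reach that student at the visit where the change is detected.

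What is at stake is participant care, not inference. Whoever implements the rule must decide whether to condition the offer on earlier status, and the present wording points towards doing so. The 2-year visit is the last assessment, so someone missed there has no later visit at which to be picked up.

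**Working it through.** The plan states no figure to reproduce. The check is one of coverage.

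**Size of the group the wording leaves exposed.** F1 plans about 3,154 high-risk and 3,154 clinical participants with complete follow-up.

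- Total: 3,154 + 3,154 = 6,308.
- High-risk share: 3,154 / 6,308 = 50%, both arms together.

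**Who gets the general offer on the literal wording.** Anxiety, depression and eating disorders are assessed in both arms at 6 weeks, 6 months and 2 years (D1; E2 schedule), so status at each visit is known.

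| Entry | 6 weeks | 6 months | 2 years | Offer at 6 months | Offer at 2 years |
|---|---|---|---|---|---|
| Clinical | Clinical | Clinical | Clinical | Yes | Yes |
| High risk | Clinical | Clinical | Clinical | Yes | Yes |
| High risk | Not clinical | Clinical | Clinical | No | Yes |
| High risk | Not clinical | Not clinical | Clinical | Not applicable | No |
| Clinical | Not clinical | Not clinical | Clinical | Not applicable | Arguably no |

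The third row waits 24 − 6 = 18 months for this offer. The fourth row never receives it. The fifth row shows that the literal line is not simply high-risk against clinical entrants: a clinical entrant who recovered and relapsed does not obviously *remain* clinical either. The second row shows the opposite limit: a high-risk entrant already clinical at 6 weeks and still clinical at 6 months is covered.

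**What the other routes add for someone newly clinical at a visit.**

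- Both arms: a referral only if the person also endorses suicidality or meets the possible-AN criteria.
- Intervention arm, up to 6 months: coach referral, and the 6-week non-improvement rule, which is not limited to clinical entrants. Access lasts 6 months, and nothing shows coach monitoring continuing to the 2-year visit.
- Usual care: the recommendation and resource list were given at entry, so what is missed later is a repeat offer, not first access.

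**Number affected.** This would be 3,154 × (share of high-risk entrants first found clinical at the visit), plus relapsed clinical entrants, minus those reached by other routes. None of these rates is in the documents. For scale only, each percentage point of high-risk entrants is 3,154 × 0.01 ≈ 32 people over both arms before the subtraction.

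**The case against.** The strongest reply is that one loosely chosen verb is carrying too much weight. The suicidality rule and the possible-AN rule in the same section turn on current status, and so does the F3 clinical-case definition (a positive screen at the assessment). The sentence sits in a list meant to protect participants, and nothing near it states an intent to leave out new cases. The literal reading would even refuse relapsed clinical entrants, which makes it less plausible as an intention. All of this stands, and loose drafting is a likely explanation. It does not remove the ambiguity, because the sentence is operative and appears twice in the same form.

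The reply is also right that the gap is partial, as the other routes show.

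A reader might infer three stronger things that the documents do not support:

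- **A deliberate choice to withhold referral from new cases.** No text states or implies one.
- **A clean split in which any clinical entrant with the same score gets the offer and a high-risk entrant does not.** The relapse case breaks that split.
- **An identical gap in the two arms at 2 years.** The omission in the wording is the same, but its consequence is not: under D1 usual care was given information on clinical services at entry, while the intervention arm was given the program link instead.

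**Conclusion.** The point holds as a minor defect of wording in a safety rule. Read literally, the general offer at 6 months and 2 years omits, in both arms, a participant newly in the clinical range at that visit: certainly a high-risk entrant first found clinical there, arguably a relapsed clinical entrant. Half of the planned completers enter in the high-risk stratum, but how many would be affected cannot be derived from the documents.

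The conclusion rests on two things: the ordinary meaning of *remain*, and the absence of any other section that widens the general offer. If the sponsor already intends and operates a current-status rule, the practical effect is nil and only the text needs correcting.

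It would be wrong to infer that the primary analysis is affected. F3 classifies every participant by current screen regardless of entry status, and no analysis or reported result is wrong because of this sentence.

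**What to change.** In D2, 2.b Ethical Considerations and D2, 2.e Risks and Benefits, change the condition so that the offer goes to participants who *are in the clinical symptom range at that assessment, regardless of status at baseline or earlier visits*, in both arms. This covers new onset and relapse alike and matches the current-status form of the suicidality and possible-AN rules. The assessments needed are already collected at both visits.

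The cost is some extra referral offers. Those made at 6 months could slightly raise service use and slightly narrow the 2-year contrast between arms. The documents do not allow that amount to be quantified, and it should be accepted knowingly. Offers made at 2 years accompany the last assessment and cannot affect the contrast. Planned sample size and data collection are unchanged.
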